### **3.6 TREATMENT CONSIDERATIONS/EXCEPTIONS**

#### **3.6.1 Treatment Beyond Progression (“Pseudo-progression”)**

A minority of patients treated with immunotherapy such as magrolimab may derive clinical benefit despite initial evidence of progressive (PD). Patients suspected to have PD by response criteria will be permitted to continue study treatment beyond confirmed PD as measured by the appropriate evaluation criteria as long as they meet all of the following criteria as determined by the investigator:

- Investigator assessed clinical benefit such as improvement in disease-related symptoms
- Subject is tolerating therapy
- Stable performance status
- Absence of other signs and symptoms indicating disease progression
- Absence of evidence to suggest that other or alternative medical intervention or treatment is needed to treat the disease

Patients that meet the above criteria should have repeat radiographic evaluation within 6 weeks of initial investigator-assessed progression to determine whether there has been a decrease in the tumor size or continued PD.

### **3.7 POST-TREATMENT/FOLLOW-UP EVALUATIONS**

Please see the Study Calendar ([Appendix G](#)) for all applicable windows and complete information.

#### **3.7.1 30-Day Safety Follow-Up visit**

The mandatory Safety Follow-Up visit should be performed approximately 30 days following the last dose of study drug or before the first dose of new anti-cancer therapy, whichever comes first. Refer to the Study Calendar ([Appendix G](#)) for all tests and procedures to be conducted upon discontinuation of treatment and during follow-up. All AEs that occur prior to the safety follow-up visit should be recorded. See section [6.1.1](#) for documentation of AEs after study treatment has ended. The investigator or qualified designee will collect information about the new anti-neoplastic therapy initiated after the last dose of trial treatment. Once new anti-cancer therapy has been initiated the subject will move into survival follow-up.

### **3.7.2 Follow-Up Visits – Prior to Disease Progression**

Patients who discontinue trial treatment for a reason other than disease progression will move into the Follow-Up Phase and should be assessed approximately as follows: every 3 months for two years after completion of study therapy, every 6 months for years 3-5, and then annually thereafter at the discretion of the investigator. Any other evaluations and tests should be performed as clinically indicated. After 5 years of monitoring without disease progression the decision to continue further surveillance imaging, including any assessments and procedures, will be left to the discretion of the investigator.

### **3.7.3 Follow-Up Evaluations – Survival/Post Disease Progression**

Upon disease progression or initiation of other anti-cancer therapy, the subject moves into the survival follow-up phase and should be contacted about every 3 to 6 months for survival status until death, withdrawal of consent, or the end of the study, whichever occurs first; unless otherwise clinically indicated.

### **3.8 STUDY CALENDAR**

See [Appendix G](#).

### **3.9 COST AND COMPENSATION**

#### **3.9.1 Costs**

NIH does not bill health insurance companies or participants for any research or related clinical care that participants receive at the NIH Clinical Center. If some tests and procedures are performed outside the NIH Clinical Center, participants may have to pay for these costs if they are not covered by their insurance company. Medicines that are not part of the study treatment will not be provided or paid for by the NIH Clinical Center.

#### **3.9.2 Compensation**

No compensation will be provided to patients for participating in this study.

#### **3.9.3 Reimbursement**

The NCI will cover the costs of some expenses associated with protocol participation. Some of these costs may be paid directly by the NIH and some may be reimbursed to the participant/guardian as appropriate. The amount and form of these payments are determined by the NCI Travel and Lodging Reimbursement Policy.

### **3.10 CRITERIA FOR REMOVAL FROM PROTOCOL THERAPY AND OFF STUDY CRITERIA**

A safety visit will occur 30 days post last dose of study drug. Prior to removal from study, effort must be made to have all patients complete an additional safety visit 18 months after the last dose of obinutuzumab as obinutuzumab has the longest half-life out of the experimental drugs for this study. Details of additional safety visits and follow-up will continue as per Section [3.7](#).

#### **3.10.1 Criteria for Removal from Protocol Therapy**

- Disease progression
  - A patient may be granted an exception to continue on study treatment with initial radiographic progression if they meet the criteria outlined in Section [3.6](#)
  - Patient who progresses prior to initiation of venetoclax will not be removed from the protocol, but will move on immediately to the triplet therapy or safety ramp-up phase
- Completion of protocol therapy
- Intercurrent illness that prevents further administration of treatment
- Requirement for use of prohibited therapies as listed in Section [4.2](#)
- Pregnancy
- Patient requests to be withdrawn from protocol therapy
- Noncompliance with trial treatment or procedure requirements in the opinion of the investigator; such a decision/rationale will be clearly noted in the medical record
- Investigator's decision to withdraw the patient if felt to be in the best interest of the patient; such a decision/rationale will be clearly noted in the medical record

- Unacceptable adverse event(s) (see Section 3.3), unless it is felt by the Principal Investigator to be in the patient's best interests to remain on study in exceptional circumstances (e.g., discontinue offending study agents while continuing others).

All subjects, regardless of reason for discontinuation of study treatment (with the exception of withdrawal of consent; unless consent to follow-up activities is documented) will be followed for progression and survival.

### **3.10.2 Off-Study Criteria**

Patients who meet the following criteria should be discontinued from the study:

- Screen failure
- Subject requests to be withdrawn from study
- Subject is lost to follow-up
- Death
- Study is cancelled for any reason
- Permanent loss of capacity to consent

### **3.10.3 Lost to Follow-up**

A participant will be considered lost to follow-up if he or she fails to return for 3 consecutive scheduled visits and is unable to be contacted by the study site staff.

The following actions must be taken if a participant fails to return to the clinic for a required study visit:

- The site will attempt to contact the participant and reschedule the missed visit as soon as is possible and counsel the participant on the importance of maintaining the assigned visit schedule and ascertain if the participant wishes to and/or should continue in the study.
- Before a participant is deemed lost to follow-up, the investigator or designee will make every effort to regain contact with the participant (where possible, 3 telephone calls and, if necessary, an IRB approved certified letter to the participant's last known mailing address or local equivalent methods). These contact attempts should be documented in the participant's medical record or study file.
- Should the participant continue to be unreachable, he or she will be considered to have withdrawn from the study with a primary reason of lost to follow-up.

## **4 CONCOMITANT MEDICATIONS/MEASURES**

### **4.1 PERMITTED THERAPY**

All treatments that the investigator considers necessary for a subject's welfare may be administered at the discretion of the investigator in keeping with the community standards of medical care. Palliative and supportive care for the other disease-related symptoms and for toxicity associated with treatment will be offered to all patients in this trial. All concomitant medication will be recorded on the case report form (CRF) including all prescription, over-the-counter (OTC), herbal supplements, and IV medications and fluids. If changes occur during the trial period, documentation of drug dosage, frequency, route, and date may also be included on the CRF.

All concomitant medications received within 28 days before the first dose of trial treatment and 30 days after the last dose of trial treatment should be recorded.

#### **4.1.1 Growth factors**

The use of hematopoietic growth factors filgrastim and pegfilgrastim are allowed.

#### **4.1.2 Tumor Lysis Syndrome (TLS)**

##### **4.1.2.1 TLS and Venetoclax**

TLS is a risk for patients with NHL who are treated with high cell-killing agents, including venetoclax. Changes in blood chemistries consistent with TLS that require prompt management can occur as early as 6 to 8 hours following the first dose of venetoclax. The risk of TLS is a continuum based on multiple factors, including tumor burden and comorbidities. Risk is highest for those with bulky disease, elevated leukocyte count, elevated pretreatment LDH levels, compromised renal function, and dehydration. We will perform tumor burden assessments, including radiographic evaluation (e.g., CT scan), assess blood chemistry (potassium, uric acid, phosphorus, calcium, and creatinine) in all patients and correct pre-existing abnormalities prior to initiation of treatment with venetoclax.

Patients with MCL and CLL are at higher risk of TLS than FL. The risk is highest during the first 5 weeks of ramp-up. A low starting dose followed by gradual dose ramp-up allows for the tumor size to be gradually reduced and has been effective in reducing the risk of TLS. Hence, in our study, patients with MCL and CLL will undergo venetoclax dose ramped-up over 5 weeks, and the target dose will be lower than patients with FL. Limited data is available in patients with MZL and hence, as a safety measure, patients with MZL will also have venetoclax dose ramped-up over 5 weeks. Also, we believe that use of magrolimab+obinutuzumab in the window period in our study may decrease bulk of disease in most of the patients resulting in reduced risk of TLS when venetoclax is commenced.

The Cairo-Bishop Definition of TLS (clinical and laboratory) will be used in this study. See [Appendix E](#) for details. We will assess the risk for TLS based on clinical and radiological assessment (e.g., CT scan) prior to initiation of venetoclax treatment. For subjects at risk of TLS:

- Guidelines for monitoring of clinical chemistries and administration of prophylaxis for the safety ramp-up period or period of risk are delineated in [Table 19](#).
- Investigator may modify the management as s/he deems appropriate for patient's clinical condition.

**Table 19: Recommended TLS prophylaxis and monitoring during Cycle 1 of venetoclax**

| Tumor Burden   | Prophylaxis   | Blood Chemistry Monitoring  |
|---|--|--|
|   |  | Setting and Frequency of Assessments  |
| Low:
All LN <5 cm
AND
ALC <25 x10  /L                                   | Hydration:
Oral (1.5-2 L)

Anti-hyperuricemics:
Allopurinol a  | CLL, MZL and MCL:

 
Pre-dose, 6 to 8 hours, and 24 hours after the first dose of the first two weeks of safety ramp-up during C1
 
Pre-dose at subsequent ramp-up doses
 
 FL: 
 
Pre-dose, and 24 hours after the first dose of the first week venetoclax treatment
 
Pre-dose, on C1D8
 
  |
| Medium:
Any LN
5 cm to <10 cm
OR
ALC ≥25 x10  /L                     | Hydration:
Oral (1.5-2 L) and consider additional intravenous fluids as tolerated

Anti-hyperuricemics:
Allopurinol   | CLL, MZL and MCL:

 
Pre-dose, 6 to 8 hours, 24 hours after the first dose of the first two weeks of safety ramp-up during C1
 
Pre-dose at subsequent ramp-up doses
 
Consider hospitalization for patients with CrCl <80ml/min at first two ramp-up doses; see below for monitoring in hospital
 
 FL: 
 
Pre-dose, and 24 hours after the first dose of venetoclax treatment
 
Pre-dose, on C1D8 and C1D15
 
  |
| High:
Any LN
≥10 cm
OR
ALC ≥25 x10  /L
AND
any LN ≥5 cm | Hydration:
Oral (1.5-2 L) or intravenous (150-200 mL/hr as tolerated) c

Anti-hyperuricemics:
Allopurinol; consider rasburicase b if baseline uric acid is elevated | CLL, MZL and MCL:
In hospital at first dose of the first two weeks of safety ramp-up during C1. 
 
Pre-dose, 4, 8, 12 and 24 hours
 
 Subsequent ramp-up doses 
 
Pre-dose, 6-8 hours, and 24 hours
 
 FL: 
 
Pre-dose, 6 to 8 hours, 24 hours at the first dose of venetoclax treatment
 
Pre-dose, weekly on D1 of each subsequent week during Cycle 1
 
 
* Hospitalization for high risk FL and MZL patients per investigator's discretion.
 |

- a. Allopurinol 600 mg 24 hours prior to first dose of venetoclax, followed by 200 mg/m^2 (maximum daily dose of 600 mg) in divided doses daily for a minimum of first 28 days of therapy.
- b. Rasburicase 0.2 mg/kg IV 24 hours prior to the first venetoclax dose. The dose may be repeated based on laboratory or clinical abnormalities, or per discretion of the investigator.
- c. Intravenous fluids should be initiated at a rate of at least 1 mL/kg/hr (target 150-200 cc/hr; not <). Modification of fluid rate should also be considered for individuals with specific medical needs.

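### Table 19 footnote a sets a 28-day allopurinol minimum, 7 days short of the 35-day venetoclax ramp-up in MZL, MCL and CLL; at DL1 it can be met by stopping the day before the step to 400 mg (minor; cheap to fix)

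*Combined protocol and SAP*

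**What the plan says.** Table 19 is headed "Recommended TLS prophylaxis and monitoring during Cycle 1 of venetoclax". It lists allopurinol for low, medium and high tumor burden. Footnote a gives the schedule: a loading dose, "Allopurinol 600 mg 24 hours prior to first dose of venetoclax", then a weight-of-surface-area dose "in divided doses daily for a minimum of first 28 days of therapy". This is the only allopurinol duration in the document, and it is not split by histology. In the text as read, marker a is printed only on the low-burden row; the medium and high rows name allopurinol with no duration of their own.

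The text introducing the table says that it sets out "administration of prophylaxis for the safety ramp-up period or period of risk". Of MCL and CLL, the same section says "The risk is highest during the first 5 weeks of ramp-up"; MZL is given the same ramp-up as a precaution because data are limited.

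Section 2.3.2.2 gives Cycle 1 as 28 days in the FL arms and 35 days in the MZL, MCL and CLL arms (Arms 2 and 4). Tables 10 and 11 give the weekly doses. At DL1 the fifth week, Days 29 to 35, is at 400 mg after a fourth week at 200 mg. At DL(-1) both weeks are at 200 mg.

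**The concern.** A stated minimum tells staff when stopping is acceptable. Here it fits FL, which Section 4.1.2.1 places at lower TLS risk than MCL and CLL, and falls a week short in the histologies that need a ramp-up. At DL1 a patient could stop allopurinol on Day 28 in full compliance with the footnote and double the venetoclax dose on Day 29, still inside the period that the protocol calls highest risk.

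The protocol elsewhere treats a dose step as a trigger. Section 4.1.2.2.1 applies the same TLS response after a first dose and after an escalation. Section 1.2.5.1 reports that TLS in the CLL monotherapy study followed either the first dose or a ramp-up step. What is at stake is consistent preventive cover at the last step. Sample size, error rates and the dose-finding rule are untouched.

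**Working it through.** No power or sample-size formula applies; the check is a day count.

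**Inputs**
- Allopurinol minimum: 28 days (Table 19, footnote a).
- Ramp-up: 5 weeks (Section 2.3.2.2, Arms 2 and 4; Table 10).
- Weekly venetoclax doses: DL1 20, 50, 100, 200, 400 mg; DL(-1) 20, 50, 100, 200, 200 mg (Tables 10 and 11).
- FL: target dose from the first day, Cycle 1 of 28 days (Section 3.1.5, Table 11).

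**Length**
- Ramp-up: 5 x 7 = 35 days, matching the protocol's own figure.
- Shortfall: 35 - 28 = 7 days (Days 29 to 35), which is 7/35 = 20% of the ramp-up, at both dose levels.
- FL: 28 - 28 = 0 days.

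**Dose starts covered by Days 1 to 28**

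| Schedule | Dose starts (day: mg) | Covered |
|---|---|---|
| DL1 | 1: 20; 8: 50; 15: 100; 22: 200; 29: 400 | 4 of 5 (Day 29 is outside) |
| DL(-1) | 1: 20; 8: 50; 15: 100; 22: 200 | 4 of 4 |
| FL | 1: target dose | 1 of 1 |

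The Day 29 step is 400/200 = 2-fold, the same as on Days 15 and 22 and smaller than the 50/20 = 2.5-fold step on Day 8. The point is coverage, not an unusually large step.

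**Does the reading of *therapy* matter?** I count from the first venetoclax dose, because the footnote ties the loading dose to it. In Arm 2 all treatment starts in the first days of Cycle 1 and venetoclax on C1D1, so counting from study treatment also ends on Day 28. In Arm 4 venetoclax starts on study day 2 x 28 + 1 = 57. Counted from the start of study treatment, the minimum would end on study day 28, before any venetoclax. The reading used here is the more favorable to the plan.

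**Patients on the DL1 schedule** (nominal, before replacements; Sections 2.3.2.1 and 10.2)
- 400 mg not carried forward: 6, all in Arm 2.
- 400 mg carried forward: 6 (Arm 2) + 6 MZL + 12 MCL + 6 CLL (Arm 4) = 30.

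Thirty is a ceiling that assumes footnote a governs every burden row. If it governs only the low-burden row, where the marker is printed, the number is smaller, and the document gives no burden split from which to estimate it.

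**The case against.** The strongest reply is that nothing tells anyone to stop on Day 28. The figure is a minimum, the table is a recommendation, its heading spans all of Cycle 1, and "Investigator may modify the management as s/he deems appropriate". All of that stands. A reader might infer that the protocol ends prophylaxis before the last step; the documents do not support this. They permit it, no more. What remains is that the heading points to 35 days while the only number given is 28.

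Other safeguards also stand. For low and medium burden the table lists "Pre-dose at subsequent ramp-up doses", so chemistry is known before the Day 29 dose; high-burden patients also have checks at 6 to 8 and 24 hours. Hydration carries no 28-day limit. These detect a problem or reduce risk, but they do not replace the urate-lowering drug.

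By Day 29 there has been substantial prior treatment. Arm 4 patients have had the two-cycle window, which Section 4.1.2.1 says "may decrease bulk of disease in most of the patients resulting in reduced risk of TLS when venetoclax is commenced". Arm 2 has no window, but its patients are scheduled for four weeks each of obinutuzumab-magrolimab treatment and rising venetoclax by then.

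The clinical evidence in the document is mostly reassuring. In the venetoclax-obinutuzumab CLL study of Section 1.2.7.1 (212 patients in the safety data, 5-week ramp-up to 400 mg), all 3 reported TLS cases came before venetoclax. Those patients were previously untreated, started venetoclax on Day 22 after obinutuzumab, and their allopurinol use is not described, so the comparison is indirect. In the NHL monotherapy study of Section 1.2.5.1, the three laboratory TLS cases were in bulky disease within 24 hours of initial dosing. The CLL monotherapy study there links TLS to ramp-up steps but ties no event to a step from 200 to 400 mg.

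**Conclusion.** The mismatch is real and minor. The allopurinol minimum is 7 days shorter than the ramp-up in MZL, MCL and CLL, and at DL1 one of five dose starts, the step to 400 mg on Day 29, falls outside it. At DL(-1) the same 7 days are outside but contain no step; FL is fully covered.

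The size in patients is unknown, with a ceiling of about 30 on the DL1 schedule. The clinical size is probably small, and the document gives no TLS rate for this step. Two stronger inferences should be avoided. One is that up to 30 patients would go without allopurinol: 30 counts patients on a dose schedule, not patients who would stop early. The other is that TLS would rise or the dose-finding result would be compromised: nothing in the document shows either.

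The conclusion rests on reading *therapy* as venetoclax therapy and on the nominal schedule without holds or delays. It is a cheap patient-safety clarification, not a flaw in the design.

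**What to change.** Amend footnote a so that, after the loading dose, allopurinol continues daily for at least the first 28 days of venetoclax in FL, and through the end of ramp-up (at least 35 days, C1D35 on the nominal schedule) in MZL, MCL and CLL. State that the footnote applies to the low-, medium- and high-burden rows. Tying the duration to the end of ramp-up also keeps cover in place if a hold delays a later step.

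The cost is one footnote in an amendment and 7 more days of recommended allopurinol in MZL, MCL and CLL. Investigator discretion to modify management can stay as it is.

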#### 4.1.2.2 Recommendations for Initial Management and TLS Prevention

##### 4.1.2.2.1 First Dose of Venetoclax or Dose Escalation

Within the first 24 hours after either the first dose or dose escalation, if laboratory criteria for TLS (**Table 21**) are met, the patient should be hospitalized for monitoring and the investigator notified. No additional venetoclax doses should be administered until resolution.

- Availability of emergency dialysis should be ensured

- Intravenous (IV) fluids should be initiated at a rate of at least 1 mL/kg/h rounded to the nearest 10 mL (target 150-200 mL/hr; < 50 mL/hr). Modification of fluid rate should also be considered for individuals with specific medical needs.

The management recommendations below focus on the minimum initial responses required. If a diagnosis of TLS is established, ongoing intensive monitoring and multidisciplinary management will be as per institutional protocols.

#### 4.1.2.3 For any occurrence of laboratory TLS:

- Withhold the next day's venetoclax dose. If resolved within 24 to 48 hours of last dose, resume at the same dose.
- For any blood chemistry changes requiring more than 48 hours to resolve, resume at a reduced dose.
- For any events of clinical TLS, resume at a reduced dose following resolution

In addition to the above, additional recommendations for patients with chronic lymphocytic leukemia/ small lymphocytic lymphoma receiving first dose of venetoclax:

- For potassium increase  $\geq$  0.5 mmol/L from baseline, AND  $>$  5.0 mmol/L, recheck potassium, phosphorus, uric acid, calcium, and creatinine and follow guidelines per Section **4.1.2.2.1**
- For phosphorus increase of  $>$  0.5 mg/dL AND  $>$  4.5 mg/dL, administer phosphate binder and recheck potassium, phosphorus, uric acid, calcium, and creatinine.

#### 4.1.2.4 Tumor Lysis Syndrome from Obinutuzumab (Precautions During Cycle -2 of Dose-Expansion)

TLS, including fatal TLS, has been reported with obinutuzumab. Patients with CLL or MCL who are treated with the combination of obinutuzumab and magrolimab are considered at risk of TLS if they have lymph nodes  $\geq$  5 cm or ALC  $\geq$   $25 \times 10^9/L$ , splenomegaly, renal dysfunction (Cr. Cl.  $<$  70 mL/min) or baseline clinical chemistry abnormalities consistent with TLS as per **Table 21**. Patients during dose-finding portion of the study will commence obinutuzumab in combination with venetoclax, and the guidelines outlined in Section **4.1.2** must be followed. During dose-expansion phase, however, patients will commence obinutuzumab in combination with magrolimab during Cycle -2 of the window period. CLL and MCL patients considered at risk of TLS when treated with obinutuzumab in combination with magrolimab must be treated and monitored as follows:

- Patients should receive IV or oral hydration (approximately 3 L per day recommended) starting 1 day before the first dose of obinutuzumab and should continue until and including D8 (approximately 3 L per day recommended).
- Patients should be treated with uricostatics (such as allopurinol) or urate oxidase (such as rasburicase) as per label or local guidance.
- Patients should undergo laboratory assessments for TLS (uric acid, calcium, phosphate, potassium, and creatinine) and the results must be known on the same day the sample was taken.
  - D1 of Cycle -2
  - D2 of Cycle -2
  - D3 of Cycle -2

- D8 of Cycle -2

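### In Arm 2 Cycle 1, no TLS panel is scheduled between the 24-hour venetoclax sample on Day 2 and Day 8, so at-risk CLL/MCL patients lack the Day 3 check after 900 mg obinutuzumab that the expansion window requires

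*Combined protocol and SAP*

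**What the plan says.** Two sets of TLS precautions apply to CLL and MCL patients, depending on the phase.

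- **Expansion window (Section 4.1.2.4).** Patients are at risk if they have large nodes or a high lymphocyte count, splenomegaly, creatinine clearance below 70 mL/min, or baseline chemistry consistent with TLS. For them, TLS chemistry is mandatory on Days 1, 2, 3 and 8 of Cycle -2, and "the results must be known on the same day the sample was taken".
- **Dose-finding (Arm 2).** The same section says "Patients during dose-finding portion of the study will commence obinutuzumab in combination with venetoclax" and refers to Section 4.1.2, where the schedule is Table 19. For CLL, MZL and MCL at low burden the draws are "Pre-dose, 6 to 8 hours, and 24 hours after the first dose of the first two weeks of safety ramp-up during C1", then pre-dose at later steps. The medium row has the same times. The high row has "Pre-dose, 4, 8, 12 and 24 hours", in hospital "at first dose of the first two weeks of safety ramp-up during C1".

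Table 11 (Arm 2 Cycle 1) and Table 12 (Cycle -2) give the same obinutuzumab: 100 mg on Day 1, 900 mg on Day 2, and 1000 mg on Days 8 and 15. Arm 2 adds venetoclax 20 mg daily on Days 1 to 7, then 50 mg from Day 8.

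No other schedule fills the interval. The Study Calendar (Appendix G) has chemistry on Day 1 of each cycle and refers to Section 4.1.2 for extra Cycle 1 TLS monitoring. The twice-weekly Cycle 1 test in Section 3.2.1 is a blood count, not chemistry.

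**The concern.** The sponsor judged that at-risk CLL and MCL patients need a chemistry check on the day after the 900 mg infusion. That check is absent in the phase where the same infusion is given together with a second drug that causes TLS. It is also the phase with no preceding window, which Section 4.1.2.1 hopes will reduce tumor bulk before venetoclax.

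Venetoclax-timed sampling does not by itself cover obinutuzumab. Section 4.1.2.4 acknowledges fatal TLS with obinutuzumab. Section 1.2.7.1 reports that all three TLS cases in the venetoclax-obinutuzumab CLL study arose on obinutuzumab, before venetoclax began.

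A Day 3 result could be acted on. Section 4.1.2.3 withholds the next day's venetoclax for any laboratory TLS, so a same-day Day 3 result could affect the doses on Days 4 to 7. By contrast, the hospitalization trigger in Section 4.1.2.2.1 covers only the 24 hours after a first or escalated venetoclax dose. Without a panel, a change that first appears after the 900 mg dose could go unseen while daily venetoclax continues, unless the investigator orders an unscheduled test.

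**Working it through.** The plan states no figure to reproduce. The check places the scheduled panels on the dosing calendar.

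**1. Panels by study day** (Tables 11, 12 and 19; Section 4.1.2.4)

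| Day | Obinutuzumab, both phases | Arm 2 venetoclax | Arm 2 panels, low/medium | Arm 2 panels, high | Window panels, at-risk CLL/MCL |
|---|---|---|---|---|---|
| 1 | 100 mg | 20 mg | pre-dose, 6–8 h | pre-dose, 4, 8, 12 h | yes |
| 2 | 900 mg | 20 mg | 24 h | 24 h | yes |
| 3 | none | 20 mg | none | none | yes |
| 4–7 | none | 20 mg | none | none | none |
| 8 | 1000 mg | 50 mg | pre-dose, 6–8 h | pre-dose, 4, 8, 12 h | yes |
| 9 | none | 50 mg | 24 h | 24 h | none |

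Panels on Days 3 to 7: 0 in Arm 2 at every tier, 1 in the window. Draws through Day 9: 3 × 2 = 6 (low/medium) or 5 × 2 = 10 (high) in Arm 2, against 4 in the window.

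**2. Does the 24-hour sample follow the 900 mg infusion?**

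Inputs: magrolimab priming takes 3 h ± 30 min (Section 3.2.1). Obinutuzumab starts at least 1 h after magrolimab ends (Table 11, footnote a). The rate starts at 50 mg/h and rises by up to 50 mg/h every 30 min to at most 400 mg/h (Table 13).

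- First 3.5 h: 25 + 50 + 75 + 100 + 125 + 150 + 175 = 700 mg.
- Remaining 200 mg at 400 mg/h: 0.5 h. Total 4.0 h.
- After a Day 1 infusion reaction, starting at 25 mg/h: 800 mg in the first 4.0 h, then 100 mg at 400 mg/h = 0.25 h. Total 4.25 h.
- Earliest end after magrolimab starts: 2.5 + 1 + 4.0 = 7.5 h (8.0 h with a 3 h magrolimab infusion).

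So the 24-hour sample follows the end of the 900 mg dose only if venetoclax on Day 1 was taken at least 7.5 h later in the day than magrolimab starts on Day 2. The protocol does not require that. In the low and medium tiers it would also push the 6–8 h draw on Day 1 late into the day.

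**3. Longest scheduled gap in week 1**

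- Now: Day 8 pre-dose (168 h after the first venetoclax dose) minus 24 h = 144 h.
- With a panel on Day 3 at about 48 h: 168 − 48 = 120 h, and that gap starts after the 900 mg dose.

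**4. Background rate**

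Section 1.2.7.1: 3/212 = 1.4%, exact 95% CI 0.3% to 4.1%, in previously untreated CLL.

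**The case against.** **Table 19 is denser overall.** It has more draws through Day 9 than the window, and high-burden CLL and MCL patients are in hospital for the first doses of weeks 1 and 2. At medium burden it says "Consider hospitalization for patients with CrCl" below 80 mL/min. Section 4.1.2.1 also says the team will "correct pre-existing abnormalities prior to initiation of treatment with venetoclax". All of this stands, so a reader should not infer that Arm 2 is monitored less in general. The gap is specific to the days after the 900 mg dose.

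**Other routes to a test exist.** Section 4.1.2.3 adds rechecks in CLL for potassium or phosphorus rises at the first venetoclax dose, at levels below the laboratory TLS thresholds for potassium. Section 4.1.2.1 provides that "Investigator may modify the management as s/he deems appropriate". These could prompt extra sampling, but neither schedules a panel after the 900 mg dose. The rechecks do not cover MCL or a change that first appears after the 24-hour sample.

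**Section 4.1.2 includes 4.1.2.4.** One could argue that the reference already brings the Day 3 draw into Arm 2. It does not: the heading and all four listed days specify Cycle -2, and the text contrasts that cycle with dose-finding.

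**The cited TLS cases do not point to Day 3.** In that study venetoclax began on day 22, so the period before it spans three weeks and several infusions. Onset days are not given. The cases show that obinutuzumab can cause TLS before venetoclax, not when.

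**Hydration.** A reader might also infer a shortfall confined to low-burden at-risk patients, who get 1.5–2 L orally in Arm 2 against about 3 L daily in the window. Table 19 does not support that limit. The medium row is also 1.5–2 L orally, with intravenous fluid only to be considered, and the high row allows either route. The 3 L figure is itself a recommendation. No hydration point is made here.

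**Conclusion.** The point holds in a narrow form. An at-risk CLL or MCL patient in Arm 2 receives the same 900 mg obinutuzumab dose as in the window, with venetoclax added, but has no assured chemistry panel from the 24-hour sample on Day 2 until Day 8. In the window a same-day Day 3 panel is mandatory.

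The size is one missing panel in an unstated share of 6 to 12 patients, somewhere between 0 and 12. MZL patients are outside the Section 4.1.2.4 rule. The conclusion that the 24-hour sample normally precedes the end of the infusion assumes venetoclax on Day 1 is not taken 7.5 h or more later in the day than magrolimab starts on Day 2.

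Two stronger readings are not supported. A Day 3 panel would not close the gap, because Days 4 to 7 are unscheduled in both phases. Nor do the documents show any effect on the dose decision rule of two or more DLTs in six patients. This is an inexpensive safety improvement and does not threaten the trial's conclusions.

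**What to change.** In Section 4.1.2.4 and Table 19, require a TLS chemistry panel on C1D3, with same-day results, for Arm 2 CLL and MCL patients who meet the existing Section 4.1.2.4 at-risk criteria, in addition to the Table 19 draws. The tiers and the rules for FL and MZL stay as they are.

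The cost is wording in one section and one table, plus one routine chemistry draw, and possibly one visit, in at most 12 patients. Section 3.2.1 does not fix the days of the twice-weekly Cycle 1 blood counts, so setting one of them on Day 3 would limit extra visits.
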